15.2.1 Scoring Algorithm of SF-12V2

SF-12v2 (4-week recall) consists of 12 items. Two composite summary scores, including Physical Component Summary (PCS) and Mental Component Summary (MCS), and 8 scale scores, including Physical Functioning (PF), Role Physical (RP), Bodily Pain (BP), General Health (GH), Vitality (VT), Social Functioning (SF), Role Emotional (RE) and Mental Health (MH), will be derived using the following scoring algorithm. Within each scale, if there are less than or equal to 50% of the item scores missing, the missing item score(s) will be imputed using the mean score of the non-missing items and used to calculate the scale score. If more than 50% of the item scores are missing, no imputation will be performed and the scale score will be set to missing.

Step 1: Item coding

Code the response to each item as follows such that higher score indicates better health state.

Response to Item 1

Response Choices	Precoded Item Value	Final Item Value
Excellent	1	5.0
Very Good	2	4.4
Good	3	3.4
Fair	4	2.0
Poor	5	1.0

Response to Items 2a and 2b

Respond Choices	Precoded Item Value	Final Item Value
Yes, limited a lot	1	1
Yes, limited a little	2	2
No, not limited at all	3	3

Response to Items 3a, 3b, 4a, 4b and 7

Response Choices	Precoded Item Value	Final Item Value
All of the time	1	1
Most of the time	2	2
Some of the time	3	3
A little of the time	4	4
None of the time	5	5

Response to Item 5

Response Choices	Precoded Item Value	Final Item Value
Not at all	1	5
A little bit	2	4
Moderately	3	3
Quite a bit	4	2
Extremely	5	1

Response to Items 6a, 6b and 6c

Response Choices	Precoded Item Value	Final Item Value
All of the time	1	5
Most of the time	2	4
Some of the time	3	3
A little of the time	4	2
None of the time	5	1

Step 2: Computing raw scale scores

After item recoding, a raw score is computed for each scale which is the simple algebraic sum of the final item values for all items in that scale as shown in the below table. For example, the raw score for PF scale is the sum of the final item values of items 2a and 2b.

Scale	Sum Final Item Values	Lowest and Highest Possible Raw Scores	Possible Raw Score Range
PF	Items 2a + 2b	2, 6	4
RP	Items 3a + 3b	2, 10	8
BP	Item 5	1, 5	4
GH	Item 1	1, 5	4
VT	Item 6b	1, 5	4
SF	Item 7	1, 5	4
RE	Items 4a + 4b	2, 10	8
MH	Items 6a + 6c	2,10	8

Step 3: Transforming raw scale scores

Transforming the raw scale score to a 0-100 scale using the formula below. The table above include the lowest possible and possible range of raw score for each scale.

$$\text{Transformed scale} = \frac{\text{Actual raw score} - \text{Lowest possible raw score}}{\text{Possible raw score range}} \times 100$$

For example, the transformed score for PF scale is (Raw PF score – 2) / 4.

Step 4: Standardizing transformed scale scores

Each transformed scale is standardized to a z-score using scale means and standard deviations from the 1998 general United States population as shown in the below table.

Scale	Mean	Standard Deviation
PF	81.18122	29.10558
RP	80.52856	27.13526
BP	81.74015	24.53029
GH	72.19795	23.19041
VT	55.59090	24.84380
SF	83.73973	24.75775
RE	86.41051	22.35543
MH	70.18217	20.50597

The formula for z-score transformation is:

$$Z\text{-score standardized scale} = (\text{Transformed scale score} - \text{Mean}) / \text{Standard Deviation}$$

For example, the z-score of PF scale = (Transform PF score – 81.18122) / 29.10558.

Step 5: Aggregating scale scores to compute raw component summary scores

The standardized scales are aggregated using weights (factor score coefficients) from the 1998 general United States population to derive raw component summary scores (PCS and MCS). Formulae for aggregating z-score standardized scales are:

$$\text{Raw PCS} = PF \times .42402 + RP \times .35119 + BP \times .31754 + GH \times .24954 +$$

$$VT \times .02877 + SF \times -.00753 + RE \times -.19206 + MH \times .22069$$

$$\text{Raw MCS} = PF \times -.22999 + RP \times -.12329 + BP \times -.09731 + GH \times -.01571 +$$

$$VT \times .23534 + SF \times .26876 + RE \times .43407 + MH \times .48581$$

Step 6: Standardizing composite summary scores

The raw PCS and MCS scores are standardized as follows such that the final PCS and MCS scores have values with mean 50 and standard deviation 10.

$$PCS = 50 + \text{Raw PCS} \times 10$$

$$MCS = 50 + \text{Raw MCS} \times 10$$

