6.3 Health Outcome Measures

The 12-item Short Form (SF)-12v2 health survey, a shortened version of the 36-item Short Form (SF-36) survey, is a generic assessment of health-related quality of life from the patient's perspective. It measures 8 concepts: physical functioning, role limitations due to physical health problems, bodily pain, general health, vitality (energy/fatigue), social functioning, role limitations due to emotional problems, and mental health (physiologic distress and physiologic well-being) ([Ware et al, 1996](#)). The 8 scales are aggregated into 2 summary measures: the Physical Component Summary (PCS-12) and the Mental Component Summary (MCS-12) scores, which range from 0 to 100, with higher scores indicating better quality of life.

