12.1 Scales and Questionnaires

Please refer to the Study Scales and Questionnaire Binder for reference copies of questionnaires and scales.

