10.5.3 Suicidality Assessment

The number and percentage of patients with suicidal ideation or suicidal behavior as recorded on the C-SSRS will be summarized by treatment group. The distribution of responses for most severe suicidal ideation and most severe suicidal behavior during the patient's lifetime, during the DB treatment period, and during the safety follow-up period will also be presented by treatment group for the safety population. Supportive listings will be provided and will include the patient identification number, study center number, lifetime history, and postbaseline values. Intensity of suicidal ideation, suicidal behavior type, and lethality of suicidal behavior will also be included in these listings. A listing of all AEs occurring in patients who have suicidal ideation or suicidal behavior will also be provided.

11.0 **HEALTH OUTCOMES ANALYSES**

The SF-12 will be administered at Visit 2 and Visit 6/ET.

Analysis of change from baseline in the PCS-12 and MCS-12 score at Week 6 will be analyzed using the ANCOVA (based on observed cases) that has treatment group, pooled country, ADT failure category (per CRF) as factors and the baseline value as the covariate.

The detailed algorithms for derivation of the PCS-12 and MCS-12 score are presented in Section [15.2.1](#).

12.0 **INTERIM ANALYSIS**

No interim analysis is planned for this study.

13.0 **DETERMINATION OF SAMPLE SIZE**

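### SAP 15.2.1 codes both SF-12 Mental Health items in one direction, so if one of them measures distress, as Protocol 6.3 makes very likely, it is scored backwards in MCS-12 and PCS-12

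*SAP*

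**What the plan says.** SAP 15.2.1 sets out the SF-12v2 scoring in six steps. Step 1 gives the governing rule: "Code the response to each item as follows such that higher score indicates better health state".

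Two tables in Step 1 use the same five frequency choices but run in opposite directions:

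- "Response to Items 3a, 3b, 4a, 4b and 7": *All of the time* = 1 up to *None of the time* = 5. The precoded value is kept.
- "Response to Items 6a, 6b and 6c": *All of the time* = 5 down to *None of the time* = 1. The precoded value is reversed for all three items.

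Step 2 forms the MH scale as the sum of 6a and 6c, with a possible range of 2 to 10. Steps 3 to 6 rescale, standardize and weight the scales without changing the direction of any item. If one MH item is missing, "the missing item score(s) will be imputed using the mean score of the non-missing items and used to calculate the scale score". SAP 17.0, which lists changes from the protocol, mentions no scoring change.

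Protocol 6.3 lists the eight SF-12 concepts and describes one as "mental health (physiologic distress and physiologic well-being". It also says that higher PCS-12 and MCS-12 scores mean better quality of life. The item texts are in neither document; Protocol 12.1 says "Please refer to the Study Scales and Questionnaire Binder for reference copies of questionnaires and scales".

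SAP 11.0 plans an ANCOVA for this: "Analysis of change from baseline in the PCS-12 and MCS-12 score at Week 6".

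**The concern.** The table for 6a, 6b and 6c satisfies the Step 1 rule only for items that describe a good state. MH has two items, and the protocol says the concept has two poles. If the scale covers both poles, one item asks about distress. A participant distressed all of the time then gets the best value on that item, and one never distressed gets the worst. The SAP does set direction item by item, as the opposite table for 3a, 3b, 4a, 4b and 7 shows, so a single direction for both MH items needs a reason that the documents do not give.

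MCS-12 is the mental quality-of-life summary in a depression trial, and MH carries its largest weight. If a distress item is reversed, improvement on it counts against treatment. MH also enters PCS-12.

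**Working it through.** **Inputs, all from SAP 15.2.1.** MH norm SD 20.50597; MH weight 0.48581 in MCS-12 and 0.22069 in PCS-12, as printed. Norm SD and MCS-12 weight for Vitality (VT) 24.84380 and 0.23534; Social Functioning (SF) 24.75775 and 0.26876; Role Emotional (RE) 22.35543 and 0.43407. **Assumption:** one of 6a and 6c measures distress and the other well-being.

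**1. The plan's own range.** With the shared table, 6a + 6c runs from 1 + 1 = 2 to 5 + 5 = 10, a range of 8, as Step 2 states. With one item coded the other way the range is again 2 to 10. A range check therefore cannot tell the two codings apart.

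**2. The MH scale.** MH = (6a + 6c − 2)/8 × 100.

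| State | Shared table | Distress item keeps its precode |
|---|---|---|
| Best: well-being *All*, distress *None of the time* | 5 + 1 = 6, MH 50 | 5 + 5 = 10, MH 100 |
| Worst: well-being *None*, distress *All of the time* | 1 + 5 = 6, MH 50 | 1 + 1 = 2, MH 0 |

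The two items cancel, and the best and worst coherent states score the same.

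**3. Effect on MCS-12.** One category on one MH item is 100/8 = 12.5 MH points, or 12.5/20.50597 × 0.48581 × 10 = 2.961 MCS-12 points.

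- One-category improvement on both MH items: 2.961 − 2.961 = 0, instead of 2 × 2.961 = +5.92.
- One-category improvement on distress alone: −2.96 instead of +2.96.
- Error of 50 MH points at either extreme: 50/20.50597 × 0.48581 × 10 = 11.85.
- All eight scales at best and at worst, through Steps 4 to 6: 62.39 and 16.04 when coded correctly (span 46.3); 50.54 and 27.89 with MH held at 50 (span 22.7).

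**4. Effect on PCS-12.** 50/20.50597 × 0.22069 × 10 = 5.38 points at each extreme, using the printed weight.

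**5. A general improvement.** Let every VT, SF, RE and MH item improve by one category, with the physical scales unchanged.

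- VT: 25/24.84380 × 0.23534 × 10 = 2.368
- SF: 25/24.75775 × 0.26876 × 10 = 2.714
- RE, both items: 25/22.35543 × 0.43407 × 10 = 4.854
- Sum without MH: 9.936. Adding MH: 9.936 + 5.923 = 15.859.

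The shared table gives 9.94 instead of 15.86 points, so 5.923/15.859 = 37% of the raw change is lost.

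**6. Standardized effect.** The variance of MCS-12 falls as well, so the standardized loss is smaller. Assume equal item SDs, equal shifts, a common correlation r among the six items, and no contribution from the physical scales. The item weights are w = (2.368, 2.714, 2.427, 2.427, 2.961, 2.961), with RE split over its two items; w′ is w with the last sign flipped; S = (1 − r)I + rJ. The ratio of printed to correct effect is

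[Σw′/√(w′Sw′)] ÷ [Σw/√(wSw)], with Σw′ = 9.936 and Σw = 15.859.

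It is 0.834, 0.904 and 0.952 for r = 0.3, 0.5 and 0.7.

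**7. Edge cases.**

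- *Sign reversal.* With VT, SF and RE each improving by one category, the MCS-12 change turns negative only if distress improves by more than 9.936/2.961 = 3.36 categories beyond well-being, on items with four steps. If VT, SF and RE do not move, it turns negative when distress improves more than well-being.
- *Only the distress item answered.* The missing-item rule lets it stand for both, so MH is 0 at best and 100 at worst. MCS-12 is then 38.70 for the all-best and 39.74 for the all-worst profile.

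**The case against.** The strongest objection is that the premise rests on one parenthesis. Protocol 6.3 describes a concept, in a paragraph that introduces the SF-12 as a short form of a longer survey; it does not describe items 6a and 6c. The wording is in a binder outside the documents. If neither item measures distress, the shared table is right. This stands: a reader might infer that the SAP is proven to score an item backwards, and the documents do not show that. They show a coding that satisfies Step 1 only if a two-item scale, described as covering two poles, in fact covers one.

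A reader might also say that the SAP forgets to reverse the MH items. It does not. The table reverses the precode of both; the difficulty is that it does so in the same direction for both, whereas a distress item should keep its precode.

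The larger figures also invite a stronger reading, namely that the SF-12 treatment comparison would come out with the wrong sign. That needs either an extreme gap between the two MH items or no movement on VT, SF and RE. Full reversal of MH needs the well-being item missing and the distress item answered, and the documents give no rate for this. The 11.85-point error applies at the poles, and the 37% is a raw-scale loss.

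Finally, the SF-12 lies outside the two hypothesis families in SAP 9.2 and the additional efficacy list in SAP 9.3, and stored responses can be re-scored. This limits the consequence but does not remove the conflict within Step 1.

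**Conclusion.** The point holds conditionally. SAP 15.2.1 gives 6a and 6c one coding direction, nothing later corrects it, and Protocol 6.3 makes it very likely that one of them measures distress. If so, following the SAP as printed breaks its own Step 1 rule on the scale with the largest MCS-12 weight and also moves PCS-12.

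The expected consequence is dilution of the MCS-12 difference. The standardized effect would be 83% to 95% of its correct size under the assumptions in step 6, none of which comes from the documents. Individual scores suffer more, since the all-best to all-worst span is roughly halved. Sign reversal and full MH reversal are edge cases.

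MADRS, CGI-S, their power and the gatekeeping procedure are not touched. It is worth correcting before SF-12 results are reported, but it does not bear on the trial's main conclusion.

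**What to change.** Before SF-12 scores are derived or reported:

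1. Check the wording of 6a and 6c on the administered form.
2. If one measures distress, move it to the table used for 3a, 3b, 4a, 4b and 7, so that the precode is kept (*All of the time* = 1 to *None of the time* = 5), and re-score the stored responses.
3. Test the program with a best-state and a worst-state record, each both complete and with one MH item missing. MH must be 100 and 0.
4. If neither measures distress, record that and leave the table unchanged.

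The cost is one wording check and, if needed, one item moved to a table that the SAP already prints, a small program change and a re-run of the scoring. Data collection does not change.

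### The SAP's PCS-12 formula prints a positive Mental Health weight (+.22069) that is inconsistent with its own weights; the sign should be verified and probably be negative

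*SAP*

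**What the plan says.** SAP Section 11.0 plans an ANCOVA of change from baseline to Week 6 in PCS-12 and MCS-12, and sends the reader to Section 15.2.1 for scoring: "The detailed algorithms for derivation of the PCS-12 and MCS-12 score are presented in Section" 15.2.1. Protocol Section 7.4.2 plans the same outcome.

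In Section 15.2.1, items are coded so that higher is better, the eight scales are turned into z-scores against a 1998 US reference population, and Step 5 combines them with weights that it calls factor score coefficients.

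- Raw PCS, first four terms: "PF \times .42402 + RP \times .35119 + BP \times .31754 + GH \times .24954"
- Raw PCS, last four terms: "VT \times .02877 + SF \times -.00753 + RE \times -.19206 + MH \times .22069"
- Raw MCS, first four terms: "PF \times -.22999 + RP \times -.12329 + BP \times -.09731 + GH \times -.01571"
- Raw MCS, last four terms: "VT \times .23534 + SF \times .26876 + RE \times .43407 + MH \times .48581"

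The point at issue is the end of the Raw PCS formula, "RE \times -.19206 + MH \times .22069", where RE has a minus sign and MH has none.

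Step 6 multiplies each raw score by 10 and adds 50, so that "the final PCS and MCS scores have values with mean 50 and standard deviation 10".

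The documents contain no second copy of the formula and no explanation of the positive MH weight in PCS.

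**The concern.** MH has the largest weight in the mental summary (.48581), yet as printed it also adds to the physical summary. The two scales before it, Social Functioning (SF) and Role Emotional (RE), carry printed minus signs in PCS, and all four physical scales are negative in MCS. A single dropped minus would explain the pattern.

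MH is a scale that adjunctive antidepressant treatment might be expected to move. If the sign is wrong, the PCS-12 comparison between arms is biased toward the arm with better MH. That bias is systematic, so sample size does not reduce it.

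**Working it through.** **Inputs.** The sixteen Step 5 weights and the Step 6 target of mean 50, SD 10. The correlations among the eight scales are not in the documents.

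**The plan's own figure.** The mean of 50 is reproduced with either sign, because z-scores have mean zero in the reference population. The SD of 10 cannot be reproduced directly, because it requires the scale correlations. The checks below use the weights instead.

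**1. Sums of weights.** MCS: .95768. PCS as printed: 1.39216. PCS with MH negative: 1.39216 − 2 × .22069 = .95078.

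**2. Communalities.** Assume the two weight columns B (PCS, MCS) are the scoring coefficients of two orthogonal components. The loadings are then L = B(B′B)⁻¹, and a scale's communality (the sum of its squared loadings) cannot exceed 1.

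- *As printed:* B′B = [[.5527, −.1470], [−.1470, .6299]], determinant .3265.
 - MH physical loading = (.22069 × .6299 + .48581 × .1470)/.3265 = .645
 - MH mental loading = (.22069 × .1470 + .48581 × .5527)/.3265 = .922
 - MH communality = .645² + .922² = 1.265, which is impossible
- *With −.22069:* the off-diagonal becomes −.3615 and the determinant .2175.
 - MH physical loading = (−.22069 × .6299 + .48581 × .3615)/.2175 = .168
 - MH mental loading = (−.22069 × .3615 + .48581 × .5527)/.2175 = .868
 - MH communality = .782

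| Scale | Printed: physical, mental (communality) | MH negative: physical, mental (communality) |
|---|---|---|
| PF | .714, −.198 (.550) | .846, .120 (.730) |
| RP | .622, −.051 (.389) | .812, .270 (.733) |
| BP | .569, −.022 (.324) | .758, .281 (.653) |
| GH | .474, .086 (.232) | .697, .375 (.626) |
| VT | .161, .411 (.195) | .475, .646 (.642) |
| SF | .107, .452 (.215) | .425, .671 (.630) |
| RE | −.175, .648 (.451) | .165, .784 (.642) |
| MH | .645, .922 (1.265) | .168, .868 (.782) |

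The share of variance explained rises from 45% to 68%.

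**3. Is MH the sign at fault?** Each PCS sign was flipped in turn. Flipping PF, RP, BP or RE also brings every communality below 1, so that test alone does not single out MH. But every flip other than MH leaves at least one negative loading and explains only 43% to 46%. The RE flip, for example, gives all four physical scales negative mental loadings (−.39 to −.04) and explains 43%. Only the MH flip makes all sixteen loadings positive, as one would expect when higher means better on every scale.

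**4. Size.** The sign changes raw PCS by 2 × .22069 × z(MH), which is 10 × .44138 = 4.4 PCS points per 1 SD of MH. For an assumed arm difference in MH:

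| MH difference | MH contribution as printed | MH contribution with minus | Shift |
|---|---|---|---|
| 0.2 SD | +0.44 | −0.44 | 0.9 |
| 0.3 SD | +0.66 | −0.66 | 1.3 |
| 0.4 SD | +0.88 | −0.88 | 1.8 |

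If VT, SF, RE and MH all rise by 1 SD, PCS changes by 10 × (.02877 − .00753 − .19206 + .22069) = +0.5 as printed, and by 0.5 − 4.4 = −3.9 with the minus.

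**5. SD of PCS.** If the negative-sign score has SD 10 and correlates c with MH, the printed score has raw variance 1 + 2(.44138)c + .44138². The component reading gives c = .168, so the SD is 10 × √1.343 = 11.6, and the correlation with MCS is .44138 × .868/1.159 = .33 instead of 0. At c = 0 the SD is 10.9 and at c = .3 it is 12.1; it stays at 10 only if c = −.22.

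**The case against.** **The SD is not settled.** A reader might infer that PCS-12 certainly loses its stated SD of 10. The documents do not support that. The 11.6 rests on the orthogonal-component reading, and other assumed correlation structures give mixed answers:

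- In 81 block structures with MCS held at SD 10, the printed PCS ran from 10.4 to 12.8 and the negative-sign PCS from 6.7 to 11.8; the printed one was closer to 10 in 27% of them.
- In a looser random simulation, 29% of printed-sign and 35% of negative-sign draws fell within 0.5 of 10.
- With weaker loadings allowed, the order reversed: 37% against 19%.

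This objection stands.

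**The harm can be overstated.** A reader might also infer that the trial could report a physical-health benefit that is nothing but mood improvement. That moves MH alone. RE enters negatively, and when all four mental scales rise together the printed PCS is nearly neutral (+0.5 per SD). Likewise, the 0.9 to 1.8 points are not points that MH adds: as printed it adds 0.44 to 0.88, and the rest is a subtraction that does not happen. Both remarks are right about wording. The distance from the negative-sign score is still 4.4 points per SD of MH in either scenario.

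**Orthogonality is assumed.** The SAP does not state it, and nothing there requires the two columns to have similar sums; VT is positive in both. This limits the communality check to strong internal evidence, short of proof.

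**A minus may have been lost in reading the PDF.** That cannot be excluded. It is less likely because the minus signs on SF and RE in the same formula survived, as did all four in MCS. It is a reason to check before changing.

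**Conclusion.** The positive MH weight in Step 5 is inconsistent with the rest of the SAP's weights, and a negative sign is the most coherent single correction. This rests on the orthogonal-component reading, supported by the sums of weights and the one-at-a-time sign flips.

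The 4.4-point difference per 1 SD of MH between the two versions is exact from the formula. The 0.9 to 1.8 points for an arm comparison depend on an assumed MH difference of 0.2 to 0.4 SD. The SD of about 11.6 is conditional and should not be reported as established.

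Only PCS-12 is affected. It lies outside the primary and key secondary endpoints and the gatekeeping families in SAP Section 9.2, so no alpha-controlled conclusion changes, and MCS-12 does not use this line. The documents also do not show that the analysis program contains the printed sign. The point merits correction before PCS-12 is reported, but it does not threaten the trial's main result.

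**What to change.** 1. Check the MH sign in the Raw PCS formula against the instrument's scoring manual and against the analysis program.
2. Once confirmed, change Step 5 of SAP Section 15.2.1 to MH × −.22069.
3. If PCS-12 was programmed as printed, re-derive it and re-run its Week 6 ANCOVA.
4. Add a validation record with all eight z-scores at −1. It should return PCS = 50 − 9.51 = 40.5 (the printed sign gives 50 − 13.92 = 36.1) and MCS = 50 − 9.58 = 40.4.

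The cost is one look-up, one sign in the SAP and, at most, one repeated derivation and analysis. No data collection or protocol text changes.
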